#### 7. ADVERSE EVENTS AND REPORTING PROCEDURES

#### 7.1 Potential Adverse Events

Slight irritation of the skin was observed in some animal studies and was likely related to the ethanol in the formulation.

Escalating doses of remetinostat gel were administered to different cohorts of patients to assess safety and tolerability in a Phase 1 study in patients with CTCL. A total of 18 patients with CTCL were sequentially enrolled into one of three study cohorts consisting of six patients each. Within each study cohort of six patients, 5 were randomly assigned to receive remetinostat gel and 1 was randomly assigned to receive placebo. Patients received treatment for a maximum of 28 days. Three dose levels of remetinostat gel were evaluated at 0.1%, 0.5% and 1%.

The study drug was well-tolerated. Eight patients, including one who received placebo, experienced 11 treatment-related adverse events. The adverse events consisted of a skin burning or warming sensation, paraesthesia, and contact dermatitis and were all related to topical application of study drug to the index lesion treatment sites. Ten of the treatment-related

adverse events were mild (Grade 1) and one event (contact dermatitis) was Grade 2. Only the Grade 2 event of contact dermatitis required treatment, for which topical steroid and moisturizer were applied after the patient completed the 28-day course of remetinostat gel treatment, which resolved. All treatment-related adverse events had resolved prior to the Day 42 End-of-Study visit.

There were no hematological findings among the 18 treated patients. Among the 5 clinical laboratory changes reported as adverse events and the 4 clinical laboratory values that reached ≥ Grade 2, none was related to study drug administration.

For the phase 2 study, 60 patients were randomised in a 1:1:1 ratio to three treatment regimens of remetinostat gel (1% QD, 0.5% BID and 1% BID). Patients received treatment for 6 months and could continue on treatment for a further 6 months (12 months in total) if they received clinical benefit during the first 6-month period.

Remetinostat gel at dosing regimens of 1% QD, 0.5% BID and 1% BID was generally well tolerated, with no reports of adverse events associated with systemic HDAC inhibitors. There were 2 SAEs (acute heart failure and fracture), observed during the study, considered unrelated to treatment with remetinostat.

The most common adverse events were pruritus and skin irritation.

Approximately half of the patients in each group reported AEs considered related to treatment; 4 of these met CTCAE Grade ≥ 3 for severity and all were skin-related: The rate of discontinuations due to treatment-related AEs was low, with no indication of a higher rate in the highest (1% BID) dose group. Overall, the patients who had dose reduction/interruptions due to remetinostat related skin AEs in the 1% BID dose group stayed on treatment for a long time. The CTC Grade 3 events resolved, patients wanted to stay on treatment despite these AEs (except for a single patient) and most of the patients (4 of 6) in this highest dose group who remained on drug for > 6 months received benefit, in terms of objective CAILS and/or pruritus responses.

In the current study, skin will be carefully evaluated during treatment. Patients who develop contact dermatitis caused by the strip bandage adhesive per PI determination may discontinue bandage use.

No systemic abnormalities were found at any dose level in the nonclinical studies and no treatment-related observations other than those above were noted in any clinical trial. Thus, no special precautions are anticipated.

The effect of remetinostat in pregnancy has not been studied. Similarly, excretion of remetinostat into breast milk has not been examined. Therefore, pregnant and lactating women are excluded from clinical trials at this time.

Remetinostat is considered unlikely to be a photo-irritant as remetinostat absorbs light at a maximum of 234 nm in the UV/visible spectrum and does not meaningfully absorb light above 290 nm. Photo-irritation has not been observed in clinical trials of remetinostat gel. There is no information to indicate that abuse or dependency would occur with exposure to remetinostat gel.

Detectable systemic levels of remetinostat after topical application are not anticipated.

See the Investigator Brochure for details on AEs captured to date from CTCL study.

# 7.2 Adverse Event Reporting

For guidance on reporting adverse events, refer to the Stanford Cancer Institute Clinical Trials Office Adverse Event SOP.

Adverse events will be graded according to CTCAE v5.0. Both Serious and Non-Serious Adverse Events will be clearly noted in source documentation and listed on study specific Case Report Forms (CRFs). The Protocol Director (PD) or designee will assess each Adverse Event (AE) to determine whether it is unexpected according to the Investigator's Brochure and/or protocol and related to the a) study drug or b) the investigation. All Serious Adverse Events (SAEs) will be tracked until resolution or until 30 days after the last dose of the study treatment.

All AE and SAEs will be reported to the Principal Investigator. The Stanford Cancer Institute Data and Safety Monitoring Committee (DSMC) will be informed of all SAEs. An AE is any unfavorable and unintended sign, symptom, or disease temporally associated with the use of an investigational medicinal product (IMP) or other protocol-imposed intervention, in this study topical remetinostat, regardless of attribution. This includes the following: AEs not previously observed in the subject that emerge during the protocol specified AE reporting period, complications that occur as a result of protocol-mandated interventions (e.g., invasive procedures such as biopsies); and preexisting medical conditions judged by the investigator to have worsened in severity or frequency or changed in character during the protocol-specified AE reporting period.

SAEs CTCAE Grade 3 and above, and all subsequent follow-up reports will be reported to the Stanford Cancer Institute Data and Safety Monitoring Committee (DSMC) using the study-specific CRF regardless of the event's relatedness to the investigation. Following review by the DSMC, events meeting the IRB definition of 'Unanticipated Problem' will be reported to the IRB using eProtocol within 10 working days of DSMC review, or within 5 working days for deaths or life-threatening experiences.

Female patients of childbearing potential will be instructed to immediately inform the investigator if they become pregnant during the study or within 3 months after the last application of study drug. The investigator will discontinue study drug and counsel the patient, discussing the risks of the pregnancy and the possible effects on the fetus. Monitoring of the patient should continue until conclusion of the pregnancy. Any SAEs associated with the pregnancy (eg, an event in the fetus; an event in the mother during or after the pregnancy; or a congenital anomaly/birth defect in the child) will be reported per Stanford SOPs.

Male patients will be instructed to immediately inform the investigator if their partner becomes pregnant during the study or within 3 months after the last application of study drug.

#### 8. EXPLORATIVE / CORRELATIVE / SPECIAL STUDIES

None.

# 9. STUDY CALENDAR

	Pre-treatment Day -2 to -30	Pre-treatment Day -1	Treatment Day 1	Treatment Week 4 (+/- 1 week)	Week 10 Visit* (+ 4 weeks)	Follow-up Week 12-18*	Early termination	
Remetinostat treatment			x	x	x			
Informed consent	Х							
Medical history	Х							
Concurrent meds	X							
Physical exam	Х	Х		Х	Х		Х	
Vital signs	Х	Х		Х	Х		Х	
Height	Х							
Weight	Х	Х		Х	Х		Х	
ECOG score	Х			Х	Х		Х	
Serum pregnancy test	Х							
Adverse event evaluation			X					
Tumor measurements and photographs		х		Х	x		x	
Tumor Biopsy		Х				(X)		
Patient Calls			X					

\*Week 10 visit may occur between weeks 10-14, depending on surgeon availability. Study drug will be applied for 8 weeks in total; if surgical excision is delayed, the study drug may be applied for up to 4 additional weeks (for a total of up to 12 weeks)

#### 10. MEASUREMENTS

# For clinicaltrials.gov and Stanford Clinical Trials Directory compliance

# 10.1 Primary Outcome

**Title**: Overall Response Rate (ORR)

**Description**: The primary objective of this study is to determine if topical remetinostat will reduce squamous cell carcinoma (SCC) tumor size (measured in mm²). Tumors will be measured with calipers throughout the study. The associated outcome is reported as the number of tumors who achieve a partial response (PR) or complete response (CR), and overall response (OR). CR and PR are defined below, and OR is the sum of PR and CR.

- CR = undetectable tumor lesion(s).
- PR = ≥ 30% decrease in total tumor area.

Timeframe: Up to 10 weeks

Safety Outcome?: No

#### 10.1.1 Relevant Subset

All tumors with study drug application at 80% compliance and above will be included in analysis.

#### 10.1.2 Measurement Definition

Tumor size will be measured by measuring the tumor with calipers at study visits week 0, 4, and 8.

#### 10.1.3 Measurement Methods

Tumor size will be measured with calipers and will be recorded in millimeters.

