#### 1. OBJECTIVES

# 1.1. Primary Objective

Overall response rate of SCC in subjects defined by at least a 30% decrease in SCC tumor area (in mm²) at end of study measurement as compared with baseline measurements. The threshold for positive response will be at least 30% decrease in tumor area (Note: RECIST v1.1 criteria have limited utility for SCCs under 10 mm, and will not be used for that reason).

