Preclinical studies have demonstrated a role for histone deacetylase 1 and 2 (HDAC1/2) in modulating Gli1 transcription and basal cell carcinoma (BCC) growth in cell lines and mouse models. We conducted an open-label clinical trial of the pan-HDAC inhibitor, remetinostat, as a neoadjuvant treatment for basal cell carcinoma (BCC). Participants applied topical remetinostat 1% gel three times per day under bandage occlusion to BCC(s) for six weeks prior to undergoing surgical excision. The primary outcome was overall response rate (ORR) as measured by at least a thirty percent decrease in BCC greatest diameter. In addition, tumor area was assessed as well as percent of tumors with complete response. Secondary objectives include suppression of Gli1 expression in post-treatment tumors and remetinostat tolerability. This trial has enrolled 17 BCCs tumors, ranging in baseline size from 6-25 mm greatest diameter, with enrollment goal of 30 tumors. Among the 14 BCCs that have completed the trial, the ORR is 64%. The longest tumor diameter of BCCs shrank by an average of 62%, and tumor area was reduced by an average of 70%. 43% (6) of tumors reached clinical resolution. Side effects associated with treatment included grade 1-2 eczematous reaction in 71% (10), and application site pain in 36% (5). Remetinostat gel for BCC offer a potentially effective, nonsurgical intervention for treatment of localized BCCs.

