#### 3. PARTICIPANT SELECTION AND ENROLLMENT PROCEDURES

# 3.1 Participant Eligibility Checklist

Participant Eligibility Checklist must be completed in its entirety for each subject prior to registration. The completed, signed, and dated checklist must be retained in the subject's study file and the study's Regulatory Binder.

The study coordinator, treating physician and an independent reviewer must verify that the participant's eligibility is accurate, complete, and legible in source records. A description of the eligibility verification process should be included in the EPIC or other Electronic Medical Record progress note.

Pr	otocol Title:	A Phase 2 Open-label, Single-arm Trial to Investigate the Efficacy and Safety of Topical Remetinostat Gel as Neoadjuvant Therapy in Patients Undergoing Surgical Resection of Squamous Cell Carcinoma (SCC)						
Pr	otocol Number:	IRB-49542 / OnCore TBD						
Pr	incipal Investigator:	[name], PhD						
II.	Subject Informat	ion:						
Sı	ıbject Name / ID:							
G	ender:	☐ Female						
Ш	. Study Information	on:				_		
		B-approved Contract signed						
		lusion Criteria B-approved protocol)	Yes	No	N/A	Supporting Documentation*		
1	greater than or equal	e cutaneous SCC or SCC in situ lesion to 5 mm. Non-invasive SCC lesion(s), re eligible, but must be amenable to						
2	18 years of age or old	er						
3		ly the topical remetinostat 3 times daily r with an occlusive bandage.						
4	dose of study therapy (WCBP), defined as a undergone a hystered	nancy test within 14 days prior to the first [for women of child-bearing potential sexually mature woman who has not stomy or who has not been naturally t least 24 consecutive months (e.g., who time in that period)]						
5	patients with a female agree to use acceptal pregnancy (e.g., oral; contraceptive; tubal li- contraceptive with spe	en of child bearing potential and male partner of child-bearing potential must ble methods of contraception to avoid injectable; or implantable hormonal gation; intra-uterine device; barrier termicide; or vasectomized male) before herapy and for 3 months after the rapy						

	Inclusion Criteria (From IRB-approved protocol)	Yes	No	N/A	Supporting Documentation*
	Has signed and dated the current IRB-approved informed consent document				
	Exclusion Criteria (From IRB-approved protocol)	Yes	No	N/A	Supporting Documentation*

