#### 4. TREATMENT PLAN

Adult subjects in the clinic who have one or more biopsy-proven cutaneous SCC or SCC-in situ (hereafter referred to as "SCC") lesions greater than or equal to 5 mm in diameter, at least one of which is being biopsied as a normal course of care, will be invited to participate in this trial. Eligibility of prospective participants will be confirmed, and subjects will enroll according to stated inclusion and exclusion criteria.

Screening visits may be combined with or without day 1 visit.

Prospective participants must be willing to sign a consent form. Subjects will also give consent to donate their SCC tissue for biomarker measurement and apply medication 3-times daily under bandage occlusion for 8 weeks. The anticipated bandage will be an adhesive bandage (e.g., "Band-Aid") with a non-adherent dressing, or paper tape with a non-adherent dressing.

Drug treatment: Subjects will be instructed to apply topical remetinostat to individual SCCs 3-times daily (TID) for 8 weeks. Patients will be asked to discontinue application of the medication at 8 weeks, approximately 2 weeks prior to their surgical excision(s), as dermal irritation from study drug may interfere with lesion identification at excision.

At least 1 target SCC will be identified requiring surgical excision per standard of care. In addition to being measured and photographed, this lesion(s) may be biopsied. Week 8 biopsy may be collected at the time of surgical excision of lesion(s). Histopathological evaluation of the specimen may be performed.

After an initial treatment application demonstration by the study team, treatment applications will be self-administered by the subject or a caregiver. Patients will receive oral and written administration instructions at the outset of the trial as follows:

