#### 10.1.5 Response Review

The primary outcome (tumor size) is measured in real time by a physician during the clinic visit; no radiologic images are obtained for later review in this study.

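### A 30% fall in area is only 0.82 mm per axis on a 5 mm lesion, and with no stated resolution, replicate reading or area formula, misreads of small lesions can inflate the ORR

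*Combined protocol and SAP*

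**What the plan says.** Section 1.1 sets the criterion: "The threshold for positive response will be at least 30% decrease in tumor area". Section 10.1 repeats it as "PR = ≥ 30% decrease in total tumor area", and Sections 12.1 and 12.4 use the same 30% of area. Sections 1.1 and 12.4 explain that RECIST v1.1 is set aside because it is of limited use for SCCs under 10 mm.

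Section 4 admits "lesions greater than or equal to 5 mm in diameter"; the first exclusion criterion in Section 3.1 removes lesions above 20 mm.

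On method, Section 10.1.3 reads "Tumor size will be measured with calipers and will be recorded in millimeters", and Section 10.1.5 adds "The primary outcome (tumor size) is measured in real time by a physician during the clinic visit". Sections 10.1.2 to 10.1.5 do not state the caliper resolution, the number of readings per visit, how area is derived from the readings, or whether the assessor sees earlier values. Photographs are taken (Section 4), but no role in scoring response is given for them.

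The decision rule (Section 12.6.2) is at least 9 responders among 30 per-protocol tumors, testing an ORR of 15% against 40% with 91% power at one-sided alpha 0.05. Section 12.6.3 supports the design by saying that untreated SCCs are not expected to regress.

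**The concern.** The plan sets RECIST aside because of small lesions, then carries a 30% figure over to area without discussing how precisely area can be read at those sizes. Near the entry limit the required change is under a millimeter per axis, which is close to what a caliper reading on skin may vary by. A lesion that has not changed could then be counted as a partial response.

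Section 12.6.3 addresses true spontaneous regression only. It does not cover apparent regression from measurement, and nothing in the plan says that the 15% null rate includes an allowance for it. At stake are an ORR that overstates activity in the smallest lesions and a test whose error rate, judged against true response, exceeds its nominal level.

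**Working it through.** **Inputs from the documents:** 30% of area; lesions of 5 to 20 mm; 30 tumors; cut-off 9; null 15%; target 40%.

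**Assumed, because the documents give nothing:** round lesions; independent normal reading error on each of two axes at baseline and at end of study, with SD 0.25 to 1.0 mm; one reading per axis in whole millimeters; longest baseline reading at least 5 mm; area proportional to the product of the axes (any constant cancels in the ratio).

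**1. The plan's own figure.** Exact binomial with n = 30 and cut-off 9: power at 40% is 0.906, which reproduces the stated 91%. Actual alpha at 15% is 0.028. A cut-off of 8 would give 0.070, so 9 is the right cut-off.

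**2. Geometry.** With equal shrinkage of both axes, the diameter falls by 1 − √0.70 = 16.3%.
- 5 mm lesion: 5 × 0.163 = 0.82 mm per axis
- 6 mm: 0.98 mm
- 10 mm: 1.63 mm
- 20 mm: 3.27 mm

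If readings are in whole millimeters, 5×5 read as 4×4 is 1 − 16/25 = 36%, and 6×6 read as 5×5 is 1 − 25/36 = 30.6%; both count as responses. 7×7 read as 6×6 is 1 − 36/49 = 26.5% and does not. If only one axis shrinks, it must fall by the full 30%, or 1.5 mm on a 5 mm axis.

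**3. Chance that an unchanged lesion is scored a responder** (simulation under the assumptions above):

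| True size | SD 0.25 mm | SD 0.5 mm | SD 1.0 mm |
|---|---|---|---|
| 5 mm | 0.3% | 9% | 24% |
| 6 mm | 0.1% | 2.5% | 15% |
| 8 mm | <0.1% | 1.3% | 10.5% |
| 10 mm | <0.1% | 0.1% | 4.7% |

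Finer recording alone does not remove the problem. One reading to 0.1 mm still gives 5.0% to 24.3% at 5 mm for SD 0.5 to 1.0 mm. The area formula also matters: with unrounded readings and no baseline condition, the 5 mm rate at SD 0.5 mm is 3.9% from two axes but 10.6% if area is taken from one diameter.

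**4. Reading error alone.** With all 30 lesions unchanged, SD 1.0 mm and sizes uniform over 5 to 10 mm, about 11.3% are misread as responders, and the chance of 9 or more of 30 is at most 0.5%. Over 5 to 20 mm it is about 0.0005%.

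**5. Reading error on top of a true 15%.** Let f be the misread rate averaged over sizes (uniform mix, whole millimeters). The apparent rate is then 0.15 + 0.85f. Misreads in the other direction are ignored, so the last column is an upper bound.

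| Sizes | SD (mm) | f | 0.15 + 0.85f | P(≥9 of 30) |
|---|---|---|---|---|
| 5–10 mm | 0.5 | 2.1% | 0.168 | 0.052 |
| 5–10 mm | 0.75 | 6.0% | 0.201 | 0.13 |
| 5–10 mm | 1.0 | 11.3% | 0.246 | 0.31 |
| 5–20 mm | 0.5 | 0.7% | 0.156 | 0.035 |
| 5–20 mm | 0.75 | 2.2% | 0.169 | 0.054 |
| 5–20 mm | 1.0 | 4.5% | 0.189 | 0.096 |

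The reference value without reading error is 0.028. At SD 0.25 mm with whole-millimeter readings, the bound is 0.033 for 5 to 10 mm lesions and 0.029 for 5 to 20 mm.

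**The case against.** The strongest reply is that the effect depends on quantities the documents do not give. At SD 0.25 mm it is negligible, and an SD of 1.0 mm is 20% of a 5 mm axis. The mix of lesion sizes is unknown, and lesions of 15 to 20 mm are practically immune. This stands, and it is why the result is given as a range.

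It can also be said that the 15% null refers to observed response and may already absorb some misreads. The plan does not say so, but the cut-off of 9 does protect against misreads when nothing else is happening. A reader might infer that reading error alone could make the trial positive. Step 4 shows that it almost never would.

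A reader might also infer that the plan prescribes one whole-millimeter reading by an assessor who sees the earlier values. It does not. Millimeters is a unit and not a resolution, and the sections are silent on replicates and on access to earlier readings. The defect is that silence.

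Finally, the basal cell carcinoma trial described in Section 2.2 used a stricter criterion: "The primary outcome was overall response rate (ORR) as measured by at least a thirty percent decrease in BCC greatest diameter". That equals 1 − 0.70² = 51% of area under proportional shrinkage. It is tempting to conclude that the present threshold is wrong, or that the 64% response rate there motivates this trial. The documents support neither. Area is an openly stated choice, the Rationale (Section 2.3) rests on murine and phase 1 HDAC-inhibitor data, and no comparison with 64% is planned.

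Complete response, reported separately, is hardly touched by a 1 mm misread. That is a partial safeguard, but it does not protect the primary ORR, which counts partial responses too.

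**Conclusion.** The point holds as a gap in the measurement method. It does not show that the endpoint or the decision rule is wrong. The geometry is exact for proportional shrinkage. False responses are a real possibility for lesions of about 5 to 8 mm, are small at 10 mm unless the SD nears 1 mm, and practically vanish at 15 to 20 mm. The harm is inflation added to true responses: a modestly to substantially anti-conservative test if most lesions are small and the SD is 0.5 mm or more, and little effect otherwise. All rates rest on the assumed SD, independent errors, the recording resolution and, at trial level, a uniform mix of sizes. This is a worthwhile, inexpensive improvement.

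**What to change.** Add to Sections 10.1.2 and 10.1.3: *Longest diameter and its perpendicular are each measured twice to 0.1 mm and averaged, recorded before earlier measurements are consulted; area is computed from the averaged diameters.* For SD 0.5 to 1.0 mm this lowers the false-response rate from about 9–24% to 0.8–14% at 5 mm, and from about 2.5–15% to 0.1–7% at 6 mm, provided the two readings err independently.

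In Section 12.4.2, keep the 30% area endpoint and the rule of 9 of 30 as the sole primary decision. Report, as a descriptive sensitivity result only, the ORR at a decrease of at least 30% in longest diameter. It should carry no decision weight, so that a discordant result does not blur the primary conclusion.

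The cost is about a minute more per lesion per visit with the same physician and calipers, plus one table row. The descriptive ORR is likely to be lower than the primary one, since a 30% fall in longest diameter already implies at least 30% of area unless the perpendicular grows.
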